## **5.2 REPORTING PROCEDURES**

All adverse events should be reported. Depending on the nature of the event the reporting procedures below should be followed. Any questions concerning adverse event reporting should be directed to the Chief Investigator in the first instance.

### **5.2.1 Non-serious AEs**

All such events, whether expected or not, should be recorded.

### **5.2.2 Serious AEs**

An SAE form should be completed and emailed to the Chief Investigator within 24 hours. However, hospitalisations for elective treatment of a pre-existing condition do not need reporting as SAEs.

All SAEs should be reported to the Scotland B REC (25/SS/0034) where in the opinion of the Chief Investigator, the event was:

- ‘related’, ie resulted from the administration of any of the research procedures; and
- ‘unexpected’, ie an event that is not listed in the protocol as an expected occurrence

Reports of related and unexpected SAEs should be submitted within 15 days of the Chief Investigator becoming aware of the event, using the NRES SAE form for non-IMP studies. The Chief Investigator must also notify the Sponsor of all related and unexpected SAEs.

Local investigators should report any SAEs as required by their Local Research Ethics Committee, Sponsor and/or Research & Development Office.

**[name] email: [[contact]](mailto:[contact])**

**Please send SAE forms to: Hammersmith Hospital, [name].**

**[contact] (Mon to Fri 09.00 – 17.00)**

## **6. ASSESSMENT & FOLLOW UP**

Patients will not be followed up beyond the time of their EPS procedure, as all the required data will be available at that time. The study end point will thus be at the completion of their EPS procedure. The study will end after 100 patients have been recruited or by the study end date.

**As the study protocol does not deviate from routine clinical care, no incidental findings are expected related specifically to clinical research. While incidental findings can be seen in the context of the routine clinical EPS procedure, these will be actioned by the clinical care team as is usual practice. 7.**

### **STATISTICS AND DATA ANALYSIS**

We aim to recruit 100 patients to undergo the AI algorithm prospective validation study. Based on retrospective pilot data of our accessory pathway localisation AI algorithm, we determined the accuracy of the AI algorithm to be 93% accurate and the next best manual algorithm prediction to be 77% accurate. Assuming the same accuracy in the prospective study, using a one-way two sample t-test, 91 participants would be needed to provide 90% power at the 5% significance level.

Data and all appropriate documentation will be stored for a minimum of 10 years after the completion of the study, including the follow-up period.

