## 1. INTRODUCTION

### 1.1 BACKGROUND

Accessory pathways are congenital cardiac abnormalities that can enable electrical impulses to bypass normal atrioventricular nodal conduction. This leaves patients at risk of supraventricular tachycardias and even sudden death in the case of pre-excited atrial fibrillation. The location of an accessory pathway can be definitively established by successful ablation. It is desirable to localise a suspected accessory pathway prior to an invasive electrophysiological study both to guide procedure planning and to personalise the consent process: pathway location determines much of individual procedure risk.

Accessory pathway location can be estimated from the 12-lead ECG using either human expertise or manual localisation algorithms that rely on specific ECG features. These approaches are subject to inter-operator variability and are often time consuming and difficult to perform for inexperienced users, respectively. Validation studies of these algorithms have not shown high accuracy, or even reproducibility in some cases. These studies are also problematic due to being either retrospective, using strict eligibility criteria not representative of clinical practice, or validation cases being entirely non-external.

Artificial intelligence has been increasingly investigated for its role as a high-performance predictive tool in healthcare and beyond. Machine learning algorithms can reproducibly classify medical data with very high levels of accuracy. Within cardiology, AI has been successfully applied to ECG interpretation for several cardiac conditions. Our group has developed a proof-of-concept AI algorithm for accessory pathway localisation, which has demonstrated an accuracy of 93% when retrospectively applied to 156 12-lead ECGs (left vs septal vs right).

To formally validate the real-world accuracy of this AI algorithm for accessory pathway localisation, it is imperative that: 1. The algorithm is tested **prospectively**; 2. The algorithm is tested on **consecutive** cases, avoiding cherry-picking; 3. The tested algorithm is locked such that it cannot be influenced by any new data during testing. 4. The testing cohort must include **external** cases, to avoid AI overfitting and test generalisability. These standards are essential for robust validation and to provide a genuine assessment of the accuracy for the algorithm before real-world application and use in clinical practice.

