### **3. STUDY DESIGN**

#### **3.1 RECRUITMENT**

We aim to recruit 100 patients for a prospective validation study of our AI algorithm for accessory pathway localisation. The direct care team will screen the records and identify patients followed up at Imperial College Healthcare Trust.

Patients will be contacted by members of their direct care team. This will occur either when they attend for routine appointments or during inpatient admission. The direct care team will obtain consent to share patients' information with the research care team. Once the patient has consented to their information being shared, a member of the research team will contact the patient and explain the details of the research study. The patient information leaflet will be provided to the patient via post or electronically via email with the patient's permission.

If the patient is agreeable, they will be formally consented on the day of their clinical EP study procedure by a member of the research team. Written consent will be gained prior to any data being collected or participation in the research protocol.

All patients recruited to this study must have had an ECG demonstrating manifest pre-excitation at any time prior to their EPS.

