##### **AI algorithm testing**

The AI algorithm has been trained using raw, digital 12-lead ECG data from patients with manifest accessory pathways who underwent successful ablation. The training data was labelled using associated procedure reports, fluoroscopy and electro-anatomical map data. The algorithm will output the location of an accessory pathway (left vs right, anterior vs posterior, septal vs lateral).

At commencement of the prospective validation study, the final AI accessory pathway localisation algorithm will be locked so that it cannot be trained on any new input data. This will be confirmed by an independent researcher. Using a digital 12-lead ECG as the input, the algorithm will output the categorical location of the pathway; this will be provided as a transverse axis location (left, septal, right) and a vertical axis location (anterior, mid, posterior).

Participants who agree to be recruited to the prospective validation study will undergo 12-lead ECG recordings via conventional digital ECG machines and EP recording systems during their EP study. These ECGs will be analysed at Imperial College London, where the AI algorithm will be applied to determine the AI-predicted location. At the time of their EP study, the successful ablation location will be recorded by the operating physician (estimated

from fluoroscopy). The proportion of ECGs correctly predicted by the AI algorithm, matching the operator assessment, will be the primary outcome measure of AI accuracy.

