#### **Secondary Outcome Measures**

- Sensitivity, specificity, positive and negative predictive values, and F1 score of the ECG AI algorithm for accessory pathway localisation.
- Difference in accuracy between the AI algorithm prediction and human estimation from the 12-lead ECG.
- Difference in accuracy between the AI algorithm and pre-specified, established manual localisation algorithms (Arruda, Milstein, Pambrun, Boersma, D'Avila and Chiang).
- Overall accuracy of the AI algorithm predictions, as compared to the ground truth of successful ablation location determined by fluoroscopy  $\pm$  3D mapping.
- Correlation of accessory pathway localisation by human estimation, and manual algorithm output as compared to the true location on 3D mapping

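### The 91 participants for 90% power do not follow from the named two-sample t-test, and an unpaired calculation does not fit one cohort scored by both methods

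*Protocol*

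**What the plan says.** The sample size is justified in one place, Protocol section 7 (Statistics and Data Analysis). From retrospective pilot data it reports that "we determined the accuracy of the AI algorithm to be 93% accurate" and "the next best manual algorithm prediction to be 77% accurate". It assumes that these accuracies will recur prospectively and concludes that, "using a one-way two sample t-test, 91 participants would be needed to provide 90% power at the 5% significance level". It gives no standard deviation, does not say whether 91 is a total or a per-group figure, and gives no rate at which the two methods disagree.

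The design is a single cohort. Section 3.1 says "We aim to recruit 100 patients for a prospective validation study of our AI algorithm for accessory pathway localisation", and section 6 says "The study will end after 100 patients have been recruited or by the study end date". Under section 3.2 the AI is applied to each participant's ECG and the prediction either matches the reference or does not. The comparison that the calculation addresses is a secondary outcome in section 3.4: "Difference in accuracy between the AI algorithm and pre-specified, established manual localisation algorithms". No separate group is described in which the manual algorithms would be scored.

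On the location scale, the Background reports an "accuracy of 93% when retrospectively applied to 156 12-lead ECGs (left vs septal vs right"), which fixes the scale for the 93%. No scale is given for the 77%. In the prospective study the output covers two axes: "this will be provided as a transverse axis location (left, septal, right) and a vertical axis location (anterior, mid, posterior").

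**The concern.** There are two faults in the one sentence. First, the number does not match the test named, and one-way is not a defined option for a two-sample t-test, so even the sidedness has to be guessed. Second, any two-group calculation treats the AI and manual results as coming from different patients. Here they come from the same patients, so the quantity that drives power is the proportion located correctly by only one of the two methods.

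A reader therefore cannot reproduce the 91, and cannot tell which test, sidedness or disagreement the 90% rests on. The final analysis may well be specified in a SAP. The issue here is what the protocol itself states.

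**Working it through.** **Inputs.** From section 7: p1 = 0.93, p2 = 0.77, difference 0.16, power 90%, level 5%, stated N = 91. From sections 3.1 and 6: planned N = 100, one cohort. Not given, so treated as assumptions: the SD (derived from the proportions), the sidedness (both tried) and the discordance (its full possible range).

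**Step 1: the named test.** For right/wrong outcomes the variances are 0.93 × 0.07 = 0.0651 and 0.77 × 0.23 = 0.1771.

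- SD from the mean variance: √0.1211 = 0.348.
- SD from the pooled proportion 0.85: √(0.85 × 0.15) = 0.357.

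Power comes from the noncentral t distribution with 2n − 2 degrees of freedom and noncentrality 0.16 / (SD × √(2/n)). At n = 91 per group the noncentrality is 3.10 or 3.02.

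| SD | n per group, one-sided | n per group, two-sided | Power at 91 per group, one-sided | Power at 91 per group, two-sided |
|---|---|---|---|---|
| 0.348 | 82 | 101 | 92.6% | 87.0% |
| 0.357 | 86 | 106 | 91.4% | 85.2% |

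No version gives 91. Reading 91 as the total of two groups is worse: a pooled z-test then has about 69% power one-sided and 57% two-sided.

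**Step 2: where 91 might come from.** A one-sided Fisher exact test on two independent groups has power 0.8966 at 90 per group and 0.9001 at 91, so it returns 91 per group. A paired exact one-sided McNemar test with independent errors comes very close, with 0.8998 at 91. Neither is the test named, and the protocol does not say which, if either, was used.

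**Step 3: the paired calculation.** Let c be the probability that the manual algorithm is right and the AI wrong. The probability that only the AI is right is then 0.16 + c, and

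discordance = 0.16 + 2c.

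The AI is wrong in 7% of patients, so c lies between 0 and 0.07 and discordance between 0.16 and 0.30. With independent errors c = 0.07 × 0.77 = 0.0539, and discordance is 0.2678. At 0.30 the two methods are never wrong together, and the correlation of their errors is −(0.07 × 0.23) / √(0.0651 × 0.1771) = −0.15.

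McNemar power was obtained by full enumeration. The number of discordant patients is binomial (N, discordance). Given that number, the count favouring the AI is binomial with probability (0.16 + c) / discordance.

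| N | Test | Discordance 0.16 | 0.2678 (independent) | 0.30 |
|---|---|---|---|---|
| 91 | exact, one-sided | 99.9% | 90.0% | 86.0% |
| 91 | exact, two-sided | 99.8% | 82.3% | 76.5% |
| 91 | z, one-sided | >99.9% | 92.9% | 89.6% |
| 91 | z, two-sided | >99.9% | 88.1% | 83.4% |
| 100 | exact, one-sided | >99.9% | 92.5% | 89.2% |
| 100 | exact, two-sided | 99.9% | 86.1% | 80.9% |
| 100 | z, one-sided | >99.9% | 94.7% | 92.0% |
| 100 | z, two-sided | >99.9% | 90.9% | 86.6% |

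Patients needed for 90% power at discordance 0.16 / 0.2678 / 0.30:

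- exact, one-sided: 48 / 92 / 103
- exact, two-sided: 56 / 112 / 126
- z, one-sided: 32 / 81 / 93
- z, two-sided: 40 / 97 / 113

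With 100 patients, 90% power holds up to a discordance of about 0.29 (exact, one-sided), 0.24 (exact, two-sided) and 0.27 (z, two-sided), and over the whole range for the one-sided z-test.

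**The case against.** The strongest reply is that little is at stake. One-way most plausibly means one-sided. On that reading the named test needs only 82 to 86 per group, so 91 is if anything generous, and the Fisher match suggests a mislabelled test rather than a baseless number. With one-sided testing, 100 patients retain at least 89.2% power on every paired reading. The lowest figures require that the two methods never fail on the same ECG. If difficult ECGs tend to defeat both methods, discordance falls below the independence value and power rises. Most of the values under 90% at N = 100 come from testing two-sided, not from the pairing itself.

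Much of this stands, and it limits the consequence: the planned size may well be adequate. It does not rescue the sentence. The Fisher match is an inference, and it would mean 91 in each of two independent groups, 182 patients in all, in a study with no second group. That the named test would need fewer than 91 per group one-sided says nothing about a single paired cohort. Sidedness is exactly what the wording leaves open, and the protocol offers no discordance from which to argue that the favourable part of the range applies.

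It is also fair to say that a corrected sentence would still size the study on a secondary comparison, whereas the primary measure is AI accuracy against the operator's assessment. That is a separate matter, which this correction does not settle.

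**Conclusion.** The sentence is wrong as written. The stated 91 is not the result of the stated test on any reading, and the test presupposes two independent groups that the study does not have. Whether 91 patients give 90% power depends on unstated choices: across the possible discordance, exact McNemar power at 91 runs from 86.0% to 99.9% one-sided and from 76.5% to 99.8% two-sided.

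This rests on the section 7 accuracies holding on a common location scale, and on the AI and manual algorithms being scored on the same patients. The latter is inferred from the single cohort and the secondary outcome, not stated outright. It is not a finding that the study is too small. It should be fixed because this is the only justification of the sample size.

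**What to change.** Replace the sample-size sentence in section 7 with a paired calculation, for example:

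> Assuming that, in the same patients, the AI algorithm is correct in 93% and the next best manual algorithm in 77% [location scale, the same for both], and that [x]% of patients are correctly located by only one of the two, a McNemar test ([exact/z]) at the [one-/two-]sided 5% level has [y]% power with 91 evaluable patients and [z]% with 100.

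Take x from the retrospective pilot, where both methods' results on the same ECGs would give it directly. If they are not available, report power over discordance of 16% to 30%. Before filling in the scale, confirm that the 77%, like the 93%, is left/septal/right accuracy.

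The cost is one reworded sentence and a short recalculation. Restating the power at the planned 100 needs no extra patients and no change in conduct, but the figure may become a range or fall below 90%. Insisting on 90% under a demanding choice would be different: a two-sided exact test with independent errors, for instance, would need 112 patients.

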## **8. REGULATORY ISSUES**

### **8.1 ETHICS APPROVAL**

The Study Coordination Centre has obtained approval from the Scotland B REC (25/SS/0034) and Health Research Authority (HRA). The study must also receive confirmation of capacity and capability from each participating NHS Trust before accepting participants into the study or any research activity is carried out. The study will be conducted in accordance with the recommendations for physicians involved in research on human subjects adopted by the 18th World Medical Assembly, Helsinki 1964 and later revisions.

### **8.2 CONSENT**

Consent to enter the study must be sought from each participant only after a full explanation has been given, an information leaflet offered and time allowed for consideration. Signed participant consent should be obtained. The right of the participant to refuse to participate without giving reasons must be respected. After the participant has entered the study the clinician remains free to give alternative treatment to that specified in the protocol at any stage if he/she feels it is in the participant's best interest, but the reasons for doing so should be recorded. In these cases the participants remain within the study for the purposes of follow-up and data analysis. All participants are free to withdraw at any time from the protocol treatment without giving reasons and without prejudicing further treatment.

Children from 13 to 17 years old will also be recruited as part of this study. Separate patient information sheets and consent forms will be provided to children depending on their age to meet their language comprehension level. One will be aimed for 13-15 year olds, and one for 16-17 year olds. Children aged 13-15 years old will be provided a tailored information sheet with simpler language. They will be consented with their parental guardian present, who will be able to consent on the behalf of the child. Children aged 16-17 years old will be provided with a separate tailored information sheet but will be able to consent for themselves.

### **8.3 CONFIDENTIALITY OF RECORDS:**

The Chief Investigator will preserve the confidentiality of participants taking part in the study and is registered under the Data Protection Act.

### **8.4 INDEMNITY**

Imperial College London hold negligent harm and non-negligent harm insurance policies which apply to this study.

### **8.5 SPONSOR**

Imperial College London will act as the main Sponsor for this study. Delegated responsibilities will be assigned to the NHS trusts taking part in this study.

### **8.6 FUNDING**

Innovate UK are funding this study.

### **8.7 AUDITS**

The study may be subject to inspection and audit by Imperial College London under their remit as sponsor and other regulatory bodies to ensure adherence to GCP and the UK Policy Framework for Health and Social Care Research

**9. STUDY MANAGEMENT**

The clinical day-to-day management of the study will be co-ordinated by [name].

**10. PUBLICATION POLICY**

Our aim to publish in a major international cardiology journal and present at international cardiology conferences.
